7.1. Magnetic resonance imaging protocol

The magnetic resonance imaging (MRI) protocol used for treatment planning and during imaging follow-up should generally follow the recommendations of the brain tumor imaging protocol for clinical trials in brain metastases (BTIP-BM) (Kaufmann et al. 2020).

In addition to the BTIP-BM recommendations, **vendor-specific 3D distortion correction for gradient non-linearity-related distortions is mandatory** and distortions due to magnetic field inhomogeneity should be minimized by patient-specific active shimming and appropriate pixel bandwidths. Distortion correction is required for both precise radiotherapy treatment delivery and exact response and progression assessment during imaging follow-up.

7.2. Principles of Assessment

Differentiation between radionecrosis and local progression:

Following stereotactic radiotherapy, it can be difficult to differentiate true tumor progression from radiation necrosis (Chao et al. 2013, Lin et al. 2015, Soffietti et al. 2017). Frequently, a definitive differentiation is only possible with longer imaging follow-up or histologic diagnosis. Due to the large initial size of metastases included in this trial, surgical resection, if possible, constitutes the best diagnostic and therapeutic approach in the case of sustained or symptomatic enlargement and is therefore generally encouraged. As recommended in the *RANO-BM* guidelines, an algorithm (see Section 8.3.) is prespecified in the FSRT Trial to provide differentiation between radionecrosis and progression and enable standardized management in the case of an enlarging lesion.

Criteria used for assessment:

The *RANO-BM* criteria are used in the FSRT Trial for the definition of progression (Lin et al. 2015). As the assessment of local control is the primary aim of the FSRT Trial, only lesions treated as part of the trial are used for the definition of progression in accordance with the *RANO-BM* guidelines for localized therapy trials. For the same reason, corticosteroid use, and clinical status are not used for the definition of local control in this trial.

Assessment if multiple brain metastases are treated in the FSRT Trial:

If multiple brain metastases are treated in the FSRT Trial, local control or radionecrosis will first be determined for each metastasis treated in the trial according to the criteria described in 7.3. and the algorithm for the differentiation between radionecrosis and progression provided in 7.4. If at least one metastasis fulfills the criteria for progression or radionecrosis, this is scored as an event, i.e. as progression or radionecrosis event on a patient

level. If at least one metastasis fulfills the criteria for progression and at least one fulfills the criteria for radionecrosis, this is scored as both a progression and a radionecrosis event on a patient level. This definition is used as it is better suited for the assessment of efficacy and tolerability of multiple local treatments than a combined metric.

7.3. Methods and criteria for efficacy evaluation

Imaging studies for the determination of tumor control will be performed as specified in the Examination Schedule. In addition to MRI-based radiotherapy planning, MRI studies will first be performed 6 weeks after the last RT treatment and then every 3 months thereafter in accordance with the general guidelines for routine diagnostic imaging in the absence of progression or clinical symptoms. Imaging intervals may need to be shortened, if an increase in size has occurred (see below). If the patient develops any signs or symptoms suspicious of progression or radionecrosis an MRI should be performed promptly.

Primary endpoint: Local control and radionecrosis according to unidimensional criteria

Local progression is defined according to the *RANO-BM* criteria by an increase of at least 20% in the longest diameter of the metastasis relative to nadir or baseline. In addition to the relative increase of 20% the lesion must increase by an absolute value of 5 mm or more.

If a metastasis has fulfilled these criteria for progression but shows spontaneous regression during subsequent imaging follow-up back to baseline or nadir diameter or a relative decrease in the longest diameter of at least 30% compared to the maximum size during enlargement, this will be scored as radionecrosis instead of progression (see 8.3). A decrease in diameter of at least 30% corresponds to the *RANO-BM* criteria for partial response in brain metastases. The date of the event will be backdated to the first imaging showing an increase in largest diameter of at least 20% and 5 mm or more. Similarly, if a metastasis shows regression according to the above-mentioned criteria after initiation of treatment for suspected radionecrosis (e.g. corticosteroids, Bevacizumab), this will also be scored as radionecrosis.

It is possible for a lesion to experience radionecrosis first, e.g. a transient increase in diameter followed by a spontaneous regression according to the above-mentioned criteria, and true progression, e.g. an increase in diameter without spontaneous regression, during subsequent follow-up.

If a tissue sample is obtained from a metastasis treated as part of the trial, the histology will be classified as "radionecrosis", "viable tumor" or "both" as has been done in the RTOG 9005 trial (Shaw et al. 2000). If the histology shows radionecrosis or viable tumor, this will be scored as radionecrosis or progression, respectively independent from any imaging metrics. In the case of radionecrosis, this will be scored as radionecrosis event, in the case of

viable tumor, this will be scored as progression event and in the case of viable tumor and radionecrosis, this will be scored as both radionecrosis and progression event. The time of the respective event will be backdated to the first imaging showing an increase in largest diameter of at least 20% and 5 mm or more. If no increase in size has occurred, the date of the procedure will be the date of the event.

If multiple brain metastases are treated as part of this trial, local progression is defined as at least one metastasis fulfilling the criteria for progression and radionecrosis is defined as at least one metastasis fulfilling the criteria for radionecrosis.

Secondary endpoint: Local control and radionecrosis according to volumetric criteria

Progression will be defined as a 72.8% increase in tumor volume, corresponding to a 20% increase in diameter of a perfect sphere, using volumetric criteria derived from the *RANO-BM* criteria.

If a metastasis has fulfilled these criteria for progression but shows spontaneous regression during subsequent imaging follow-up back to baseline or nadir volume or a relative decrease in tumor volume of at least 65.7% compared to the maximum volume during enlargement, this will be scored as radionecrosis instead of progression (see 8.3.). A relative decrease in metastasis volume of 65.7% corresponds to a 30% decrease in diameter of a perfect sphere and conforms with the criteria for partial volumetric response proposed by the *RANO-BM* working group. The date of the event will be backdated to the first imaging showing an increase in tumor volume of at least 72.8%. Similarly, if a metastasis shows regression according to the above-mentioned criteria after initiation of treatment for suspected radionecrosis (e.g. corticosteroids, Bevacizumab), this will also be scored as radionecrosis.

It is possible for a lesion to experience radionecrosis first, e.g. a transient increase in volume of 72.8% or more followed by a spontaneous regression, and true progression, e.g. an increase in volume without spontaneous regression, during subsequent follow-up.

If a tissue sample is obtained from a metastasis treated as part of the trial, the histology will be classified as "radionecrosis", "viable tumor" or "both" as has been done in the RTOG 9005 trial (Shaw et al. 2000). If the histology shows radionecrosis or viable tumor, this will be scored as radionecrosis or progression, respectively independent from any imaging metrics. In the case of radionecrosis, this will be scored as radionecrosis event, in the case of viable tumor, this will be scored as progression event and in the case of viable tumor and radionecrosis, this will be scored as both radionecrosis and progression event. The time of the respective event will be backdated to the first imaging showing an increase in tumor volume of at least 72.8%. If no increase in size has occurred, the date of the procedure will be the date of the event.

If multiple brain metastases are treated as part of this trial, local progression is defined as at least one metastasis fulfilling the criteria for progression and radionecrosis is defined as at least one metastasis fulfilling the criteria for radionecrosis.

Distant brain failure:

Distant brain failure is defined in accordance with the *RANO-BM* guidelines as the appearance of new or progressive lesions distant from the metastases treated as part of the trial.

Distant lesions will be defined as having no direct contact to the initial volume of the metastases treated in the trial as determined by rigid coregistration of the baseline MRI to the follow-up MRI during central review.

Cause of death:

Cause of death will be determined for brain-metastasis specific survival as "death associated with brain metastases" and "death not associated with brain metastases". Mandatory criteria for death associated with brain metastases are progressive neurologic dysfunction and local progression as per the criteria described above or progressive neurologic dysfunction and distant brain failure.

Additional Assessments:

The following assessments, examinations and questionnaires will be completed at all visits: The ECOG Performance Status will be used to assess the patient's general health. Adverse events and toxicities identified by querying the patient will be documented based on the Common Terminology Criteria for Adverse Events (NCI CTCAE Version 5.0). The patient's quality of life will be assessed using the EORTC QLQ-C30 and EORTC QLQ-BN20 quality of life questionnaires. Corticosteroid use and current systemic therapies will be documented.

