1.6.2. Secondary objectives

- Improvement of the tolerability of local radiotherapy, as measured based on the endpoints CNS toxicity and, in particular, radiation necrosis in accordance with the Common Terminology Criteria for Adverse Events Version 5.0. Improved tolerability will also be measured as time to radiation necrosis.
- Improvement of the local control of irradiated brain metastases, as determined based on volumetric criteria. Volumetric criteria may have

important methodological advantages over traditional endpoints for the identification of treatment failure, especially in the case of large brain metastases. This study aims to improve our understanding of volumetric criteria and helps to further establish them.

Based on the *RANO-BM* criteria, progression is defined as an increase in volume of 72.8% or more (corresponds to a 20% increase in diameter for a perfect sphere). True local progression and radionecrosis are differentiated via a prespecified algorithm in the trial. If multiple metastases are treated in the trial, progression is defined as at least one metastasis fulfilling the criteria for progression.

- Assessment of quality of life (EORTC QLQ-C30 and QLQ-BN20)
- Improvement of local progression-free survival
- Improvement of overall survival
- Improvement of brain metastases-specific survival
- Time to distant brain failure

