7.4. Algorithm in the case of an enlarging lesion

As soon as a lesion treated in the trial shows an increase in maximum diameter of at least 20 % and 5 mm or more compared to baseline or nadir diameter during central review of imaging data, this is preliminary scored as progression and the patient enters this algorithm. The aim of this algorithm is to provide definitive differentiation between radionecrosis and progression and to enable standardized management in the case of an enlarging lesion.

Glucocorticoid-resistant symptoms:

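### The volumetric progression rule (+72.8%) keeps only the relative half of the primary criterion and names no reference volume, so lesions that have shrunk well below 1 cm can be scored as progressed on a change of about 1 mm

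*Protocol*

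**What the plan says.** Primary endpoint (protocol, section 7.3): local progression needs "an increase of at least 20% in the longest diameter of the metastasis relative to nadir or baseline", and then: "In addition to the relative increase of 20% the lesion must increase by an absolute value of 5 mm or more". Both parts must be met.

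Volumetric secondary endpoint (sections 1.6.2 and 7.3): in the objectives, "progression is defined as an increase in volume of 72.8% or more (corresponds to a 20% increase in diameter for a perfect sphere"). Section 7.3 repeats the threshold ("Progression will be defined as a 72.8% increase in tumor volume, corresponding to a 20% increase in diameter of a perfect sphere") and describes it as derived from RANO-BM. Neither place gives an absolute minimum, and neither says what the increase is measured against. A nadir reference is only implied, by the rescoring clause. Under that clause an enlarged lesion becomes radionecrosis if it later goes "back to baseline or nadir volume or a relative decrease in tumor volume of at least 65.7% compared to the maximum volume during enlargement". On dating: "The date of the event will be backdated to the first imaging showing an increase in tumor volume of at least 72.8"%.

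Section 1.6.2 says the prespecified algorithm separates volumetric progression from radionecrosis. Section 7.4 opens that algorithm only when a lesion "shows an increase in maximum diameter of at least 20 % and 5 mm or more compared to baseline or nadir diameter".

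**The concern.** The volumetric rule is offered as the volume form of the primary rule, but only the percentage was converted. The 5 mm part is what stops a small residual lesion from being called progressive on a trivial change, and nothing takes its place. Treated lesions are expected to shrink. If nadir is the reference, the threshold shrinks with them, while the contouring error need not.

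An enlargement that meets only the volumetric rule does not enter the section 7.4 algorithm, so the separation promised in section 1.6.2 is not available for it. One lesion is enough for a patient-level event.

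False events would fall mainly on lesions that responded best. Spread equally over the arms, they dilute the volumetric comparison. If one arm shrinks lesions more, they could bias it. They also confound a stated aim of the trial, to learn whether volumetric criteria detect failure better than unidimensional ones. Earlier volumetric detection could not be told apart from a looser threshold.

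**Working it through.** **Plan's own figures.** For a sphere, V = πd³/6. Then 1.2³ − 1 = 72.8% and 1 − 0.7³ = 65.7%. Both reproduce.

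**Where the two rules diverge.** For a sphere of reference diameter d, the volumetric rule fires at growth of 0.2d. The primary rule needs the larger of 0.2d and 5 mm. These are equal when 0.2d = 5, that is at d = 25 mm. The volume equivalent of +5 mm is ((d + 5)/d)³ − 1.

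| Reference d (mm) | Growth for +72.8% (mm) | Growth for primary rule (mm) | Volume increase at +5 mm |
|---|---|---|---|
| 4 | 0.8 | 5 | 1039% |
| 5 | 1.0 | 5 | 700% |
| 8 | 1.6 | 5 | 329% |
| 10 | 2.0 | 5 | 237.5% |
| 15 | 3.0 | 5 | 137% |
| 20 | 4.0 | 5 | 95.3% |
| 25 | 5.0 | 5 | 72.8% |

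Lesions enter at 10 to 40 mm in longest diameter (section 3.1). Section 4.4.1 limits the slice thickness of the MRI for target delineation to 1 mm. Growth that triggers the volumetric rule is at or below that figure only for references of 5 mm or less. If the reference volume is zero, the percentage increase is unbounded.

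**False events on a stable lesion.** The protocol gives no contouring error, so these inputs are assumed:
- independent normal error on equivalent-sphere diameter, SD 0.2, 0.3 or 0.5 mm;
- a lesion truly stable at its nadir size from the first follow-up scan;
- comparison with the smallest volume so far.

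The examination schedule gives 5 scans by 12 months and 9 by 24 months. The probability of at least one false volumetric progression per lesion, by simulation, is:

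| Nadir (mm) | SD 0.2: 5 / 9 scans | SD 0.3: 5 / 9 scans | SD 0.5: 5 / 9 scans |
|---|---|---|---|
| 4 | 4% / 12% | 27% / 57% | 65% / 93% |
| 5 | 0.6% / 2% | 12% / 30% | 50% / 83% |
| 6 | 0.1% / 0.2% | 4% / 12% | 36% / 68% |
| 8 | 0% / 0% | 0.3% / 1% | 14% / 35% |

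Under the same error, the primary rule's 20% and 5 mm gave 0% in every cell.

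**How many are later rescored as radionecrosis.** Rescoring was counted on a return to the nadir or a fall of 65.7% from the maximum. At a 5 mm nadir, the share of false events rescored within 5 / 9 scans is about 2% / 3% at SD 0.2 mm, 6% / 13% at SD 0.3 mm and 16% / 34% at SD 0.5 mm. The rest stay progression.

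**Effect of a 2 mm minimum in equivalent diameter.** Over 9 scans, false events fall to 0% (at most 0.01%) at SD 0.3 mm or less, and to about 6% at SD 0.5 mm.

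**The case against.** Deriving a rule from RANO-BM is not the same as claiming equivalence to it. Leaving out a linear 5 mm floor may be deliberate for a measure meant to detect failure early. The endpoint is secondary and descriptive (section 9.4) and reading is central and blinded (section 7.5). Shrinkage to 5 mm means losing 1 − (5/10)³ = 87.5% of volume from 10 mm, and 1 − (5/20)³ = 98.4% from 20 mm. If the nadir is reached only at 6 months, 3 scans remain by month 12, and the SD 0.3 mm figures fall to 11% at 4 mm and 4% at 5 mm. The 9-scan figures need survival to 24 months, while section 9.2 expects about half the patients to be dead at 12. Measurability rules for very small lesions often sit in a SAP.

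All of this limits the size, and it stands. It does not remove the point. The protocol itself fixes the threshold, the rescoring and the dating, and blinding does not reduce measurement noise.

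A reader might also infer more than the documents support:
- *That any treated lesion is exposed to sub-millimetre noise.* At entry sizes, 2 to 8 mm of growth is needed. From 25 mm upward the missing minimum changes nothing.
- *That false progression routinely turns into false radionecrosis.* On a return to nadir, usually only a minority does. A literal reading of the return to baseline would be met at once by a lesion still below baseline. That is an ambiguity in the clause, not a stated rule.
- *That the missing confirmatory scan sets this endpoint apart.* The primary rule requires none either.
- *That a power loss or a diluted hazard ratio can be quantified.* The protocol gives neither the share of patients with false events nor a planned power for this endpoint.

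**Conclusion.** The point holds for lesions that shrink well below 1 cm. The text fixes a relative-only threshold with no stated reference, and the enlarging-lesion algorithm does not catch what it lets through. The divergence from the primary rule below 25 mm is arithmetic and needs no assumption. The false-event rate does. At a 5 mm nadir over five scans it runs from about 0.6% (SD 0.2 mm) to 50% (SD 0.5 mm), given a lesion already stable at that size and a nadir reference. How many lesions reach such sizes cannot be read from the protocol.

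The primary endpoint, its test and the sample size are untouched. The change is worth making because the trial wants to establish volumetric criteria, and this rule would blur that comparison.

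**What to change.** In sections 1.6.2 and 7.3:

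1. Name the reference as the smallest volume so far, baseline or nadir, and use the same reference in the rescoring clause.
2. Require at least +72.8% and an absolute minimum that is never stricter than the primary rule's 5 mm. An example is an increase of at least 2 mm in equivalent-sphere diameter, which is 20% of the 10 mm entry limit. For a vanished lesion, the absolute part alone applies.
3. Apply the same two-part condition to the enlargement that starts volumetric radionecrosis scoring, and to backdating.
4. Reconcile section 1.6.2 with section 7.4 by saying how enlargements that meet only the volumetric rule are adjudicated for scoring.
5. Report the relative-only rule as a sensitivity analysis.

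A fixed volume floor such as 0.38 cm³ (72.8% of a 10 mm sphere) is not a good substitute. Eligibility is by longest diameter, so a 10 × 7 × 7 mm lesion (0.257 cm³) would need 0.381/0.257 − 1 = 48% more than its own volume on top of doubling, about +149%, at baseline. From a 4 mm nadir it would need +5.25 mm, more than the primary rule. The 2 mm minimum also binds on that 10 × 7 × 7 mm lesion, but less: its equivalent diameter is 490^(1/3) = 7.88 mm, so it needs (9.88/7.88)³ − 1 = 97%.

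The cost is wording only, since the volumes are measured anyway. True regrowth of a very small residual lesion is called slightly later on this endpoint, for example at 7 mm rather than 6 mm from a 5 mm nadir.

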7.4. Algorithm in the case of an enlarging lesion

As soon as a lesion treated in the trial shows an increase in maximum diameter of at least 20 % and 5 mm or more compared to baseline or nadir diameter during central review of imaging data, this is preliminary scored as progression and the patient enters this algorithm. The aim of this algorithm is to provide definitive differentiation between radionecrosis and progression and to enable standardized management in the case of an enlarging lesion.

Glucocorticoid-resistant symptoms:

If the patient shows neurologic symptoms that are resistant to glucocorticoid treatment or if the patient is symptomatic and glucocorticoid treatment is contraindicated, resection of the enlarging lesion is advised. Resection will provide definitive histologic diagnosis. Histology will be classified as "radionecrosis", "viable tumor" or "both" as has been done in the RTOG 9005 trial (Shaw et al. 2000). In the case of radionecrosis, this will be scored as radionecrosis event, in the case of viable tumor, this will be scored as progression event and in the case of viable tumor and radionecrosis, this will be scored as both radionecrosis and progression event. The time of the respective event will be backdated to the first imaging showing an increase in largest diameter of at least 20% and 5 mm or more. If resection is not possible or if the patient denies surgery, stereotactic biopsy is recommended. Scoring will be performed as mentioned for resection. If stereotactic biopsy is not possible, an amino acid or FDG-PET coregistered to MRI is recommended. In the case of findings suggestive of radionecrosis on amino acid or FDG-PET a trial with Bevacizumab is advised according to Levin et al (Levin et al. 2011, Chao et al. 2013, Soffietti et al. 2017). Imaging intervals should be shortened to 6 weeks or less. If the metastasis shows regression after initiation of bevacizumab or corticosteroids or regresses spontaneously during subsequent imaging follow-up back to baseline or nadir diameter or shows a relative decrease in the longest diameter of at least 30% compared to the maximum size during enlargement, this will be scored as radionecrosis instead of progression. Else if the lesion receives additional treatment, i.e. Whole brain radiotherapy, repeat stereotactic radiotherapy or systemic treatment with established CNS effect, if the patient dies or is lost to follow-up or if routine study follow-up ends, this is scored as progression and the time of the event will be backdated to the first imaging showing an increase in largest diameter of at least 20% and 5 mm or more.

No Glucocorticoid-resistant symptoms:

In the absence of glucocorticoid-resistant symptoms, a trial with dexamethasone in a total dose of 4 – 24 mg daily depending on comorbidities and prior steroid dose is recommended. If contraindications to steroid treatment exist or if the patient is asymptomatic, imaging follow-up without initiation of steroids is possible. Imaging intervals will be shortened to 6 weeks. In the case of progressive symptoms an MRI has to be performed promptly. If short-term follow-up imaging or any subsequent imaging shows an increase in metastasis diameter of additional 20% and 5 mm or more compared to the first imaging showing the initial increase of at least 20% and 5 mm or more in diameter, it is advised to proceed as described under Glucocorticoid-resistant symptoms. Otherwise MRI follow-up will continue at 6-weeks interval. If the metastasis diameter decreases again to baseline or nadir levels or if the metastasis diameter decreases by at least 30% compared to the maximum diameter during enlargement, this is scored as radionecrosis event and the patient continues with routine study follow-up. The time of the event will be backdated to the first imaging showing an increase in largest diameter of at least 20% and 5 mm or more.

Else if the lesion receives additional treatment, i.e. Whole brain radiotherapy, repeat stereotactic radiotherapy or systemic treatment with established CNS effect, if the patient dies or is lost to follow-up or if routine study follow-up ends, this is scored as progression and the time of the event will be backdated to the first imaging showing an increase in largest diameter of at least 20% and 5 mm or more.

If it is clinically determined necessary by the treating physician deviation from the above-mentioned algorithm is possible after consultation with the Principal Investigator.

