2.4. Time schedule

Start of study:	Q3 2020
Start of recruitment:	Q1 2021
Duration of recruitment:	3 Jahre
Duration of follow-up:	2 Jahre
End of study:	2026

Follow-up is performed for progression/radionecrosis as well as for overall survival, toxicity and distant progression, respectively. In case of local progression, radionecrosis or distant progression, follow-up for the other events as well as toxicities and overall-survival continues. In case of radionecrosis, follow-up for progression continues, if not determined by histology, as progression can occur after a lesion has experienced radionecrosis. Conversely, in case of progression, follow-up for radionecrosis for the respective lesion ends.

3. Selection of study population

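### Sections 7.3 and 7.4 set different conditions for rescoring a progression as radionecrosis, and 7.4 does not say whether shrinkage after salvage treatment counts

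*Protocol*

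**What the plan says.** Section 7.3 defines the primary endpoint. A lesion that has met the growth criteria is rescored as radionecrosis if it "shows spontaneous regression during subsequent imaging follow-up back to baseline or nadir diameter", or falls by at least 30% from its maximum. One exception to spontaneity is given: regression "after initiation of treatment for suspected radionecrosis (e.g. corticosteroids, Bevacizumab), this will also be scored as radionecrosis". The volumetric rule in 7.3 has the same structure.

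Section 7.4 is the operating algorithm. On first enlargement, "this is preliminary scored as progression and the patient enters this algorithm". In the branch without glucocorticoid-resistant symptoms, a return to baseline or nadir counts as radionecrosis, as does the 30% limb: "if the metastasis diameter decreases by at least 30% compared to the maximum diameter during enlargement, this is scored as radionecrosis event". The next test reads "Else if the lesion receives additional treatment, i.e. Whole brain radiotherapy, repeat stereotactic radiotherapy or systemic treatment with established CNS effect". That test, or death, loss to follow-up or the end of routine follow-up, scores progression, backdated to the first enlargement.

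In the glucocorticoid-resistant branch the 30% limb reads "or shows a relative decrease in the longest diameter of at least 30% compared to the maximum size during enlargement". It closes a sentence about regression after bevacizumab or corticosteroids, or spontaneous regression.

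Section 2.4 adds that "in case of progression, follow-up for radionecrosis for the respective lesion ends".

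**The concern.** Two sections define the same event and do not impose the same condition. Under 7.3 the reason for the shrinkage matters. In the 7.4 branch without glucocorticoid-resistant symptoms only its size matters, and that test stands ahead of the salvage test. Shrinkage after repeat stereotactic radiotherapy or whole-brain radiotherapy may be recurrent tumour responding to salvage. If it is scored as radionecrosis, a local failure leaves TTLP, or is replaced by a later event, and is added to the radionecrosis endpoint. The trial is open and salvage is chosen by the treating team, so its use could differ by arm. Blinded central review cannot resolve a rule that gives two answers.

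**Working it through.** **One lesion under each rule.** Suppose a lesion grows by at least 20% and 5 mm at scan A, is re-irradiated at B without tissue being taken, and at scan C is at least 30% below its maximum.

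- Section 7.3: the regression is neither spontaneous nor after treatment for suspected radionecrosis. Score: progression, dated A.
- Section 7.4 in time order: at B there has been no regression and additional treatment is given. Score: progression, dated A. Section 2.4 then ends radionecrosis follow-up for that lesion.
- Section 7.4 in literal if/else-if order on the whole record: the first test is met at C, so the salvage test is not reached. Score: radionecrosis, dated A.

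No sentence chooses between the last two. Section 2.4 does not say whether a preliminary progression score is enough to end radionecrosis follow-up.

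**The plan's own sample size (Section 9.2).** Inputs: 12-month control of 65% and 80%, 50% exponential drop-out over 12 months, 12 months of follow-up, one-sided 2.5%, 80% power, 1:1 allocation.

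- Yearly hazards: SRS −ln 0.65 = 0.4308; FSRT −ln 0.80 = 0.2231; drop-out ln 2 = 0.6931. Hazard ratio 0.2231/0.4308 = 0.518.
- Event probability P(λ) = λ/(λ+0.6931) × [1 − exp(−(λ+0.6931))]: SRS 0.2587; FSRT 0.1461; at the mean hazard 0.3270, 0.2050.
- φ(λ) = λ²/P(λ): 0.7173, 0.3408 and 0.5216.
- √N = [1.960 × √(4 × 0.5216) + 0.8416 × √(2 × 0.7173 + 2 × 0.3408)] / (0.4308 − 0.2231) = 19.53, so N = 381.5. The stated 382 is reproduced.
- Expected events: 191 × (0.2587 + 0.1461) = 77. The protocol states 82; that difference is a separate matter.

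**Illustration with an assumed share q of progressions rescored, equal in both arms.** Multiplying both hazards by (1 − q) in the same formula at N = 382 gives power of 80.1% at q = 0, then 78.3%, 76.4%, 72.0% and 66.9% at q = 5%, 10%, 20% and 30%.

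Simulated log-rank tests (191 per arm, the same hazards, at least 8,000 runs per scenario) show how much depends on what happens to rescored patients:

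| Scenario | 12 months | 24 months |
|---|---|---|
| No rescoring | about 81% | about 91% |
| q = 20%, rescored patients stay event-free | about 69% | about 80% |
| q = 20%, censored at rescoring | about 72% | about 85% |
| q = 20%, resume the same risk | about 74% | about 87% |

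Radionecrosis added at q = 20% over 12 months: 0.20 × 25.9% = 5.2% of SRS patients and 0.20 × 14.6% = 2.9% of FSRT patients.

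**Direction.** If the shares were 20% SRS and 10% FSRT, the apparent hazard ratio would be 0.518 × 0.90/0.80 = 0.583. With 10% and 20% it would be 0.518 × 0.80/0.90 = 0.460. These shares are assumed too, and the sign depends on which arm has more rescoring.

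**The case against.** The strongest reply is that 7.4 describes decisions over time: serial MRI at 6-week intervals, with salvage listed beside death, loss to follow-up and end of follow-up, each of which closes observation of the lesion. If salvage did not also close it, listing salvage would add nothing, because a lesion that never regresses is scored as progression by one of the other three anyway. Section 7.3 excludes the scenario outright and describes radionecrosis as "a transient increase in diameter followed by a spontaneous regression according to the above-mentioned criteria". Patients in this branch of 7.4 receive steroids or observation, so its neutral wording may simply cover the two routes that 7.3 allows. This stands as the likelier intent. It does not remove the inconsistency, because the same list can also be read as a final default applied when no qualifying regression was ever seen, and the algorithm is presented as the means of definitive differentiation.

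A reader might infer that the algorithm, as written, sends true progressions to radionecrosis. The documents do not support that; it is one of two readings and the less natural one. Nor does the glucocorticoid-resistant branch add much, since its 30% limb sits in a sentence already limited to the 7.3 conditions.

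A reader might also infer a biased primary comparison or an inflated type I error. That needs both the literal reading and unequal rescoring between arms, and the protocol gives no rate for either arm.

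Finally, rescored patients do not necessarily leave the endpoint. Follow-up for progression continues after non-histological radionecrosis (2.4), viable tumour on histology is progression whatever the imaging shows (7.3), and another treated metastasis can still supply the event (7.2).

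**Conclusion.** The point holds as an inconsistency in the definition of the primary event: 7.3 and the 7.4 branch without glucocorticoid-resistant symptoms can score one re-irradiated, shrinking lesion in opposite ways, and no sentence decides between them. The probable intent is that such a lesion stays progression. The effect on the result cannot be sized or signed from the documents. The power figures assume that 20% of progressions are rescored in both arms and that the literal order is applied every time; the event-free case is the pessimistic end. The rule should be corrected because it decides what counts as a TTLP event, not because a bias has been shown.

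**What to change.** Reconcile 7.4 with 7.3, for both the unidimensional and the volumetric criteria, with a scoring rule along these lines: regression counts toward radionecrosis only if it is spontaneous or follows treatment for suspected radionecrosis, and only if it is seen on a scan obtained before any of the additional treatments of the lesion listed in 7.4; whichever comes first, qualifying regression or additional treatment, fixes the score, and later scans of the same episode do not change it. This leaves patient management untouched and needs no extra scans.

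The cost is one or two sentences, plus one data item. The date of any whole-brain or repeat stereotactic radiotherapy of the lesion must reach the endpoint adjudication. The visit schedule lists only systemic treatment and glucocorticoid dose, so this date is not visibly collected there. However, the salvage test in 7.4 and the censoring rule for non-protocol treatment in 9.1 already depend on it.
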